#### **4.3. Randomization**

Random assignment of participants in Part 2 of the study will use a centralized interactive response technology, in accordance with pregenerated randomization schedules. Up to 4,000 participants each in the 6 years to < 12 years, 2 years to < 6 years, and 6 months to < 2 years age groups will be randomized in a 3:1 ratio to the mRNA-1273 arm (n = up to 3,000 participants in each group) or placebo arm (n = up to 1,000 participants in each group).

#### **4.4. Blinding and Unblinding**

This study is conducted in three parts, Part 1 of this study will be open label, blinding procedures will not be applicable.

Part 2 of this study will be conducted in an observer-blind manner. The investigator, study staff, study participants, study site monitors, and Sponsor personnel (or its designees) will be blinded to the IP administered until study end, with certain exceptions, please refer to Section 8.1 of the protocol for details.

Part 3 is open label; however, if blinded administration is ongoing at the site, blinded procedure for Part 2 still applies.

The final analysis of all endpoints will be performed after all participants have completed all planned study procedures.

At the time of interim analysis, only pre-identified Sponsor and unblinded Contract Research Organization (CRO) team members as specified in the study Data Blinding Plan will be unblinded to review treatment level results and individual listings. Please also refer to [Section 6.9](#). Study sites will remain blinded to individual treatment assignments until the end of the study.

If a COVID-19 vaccine is authorized or licensed for a specific age group before the end of the study, please refer to protocol section 3.3 for unblinding and/or cross-over plans.

Participants under 6 years of age in Part 2 who have reached at least 6 months follow up after Dose 2 will be eligible for unblinding via a telephone call to learn which treatment they received. Participants who received placebo will be offered the option of cross-over vaccination with mRNA-1273 at that point as described above.

## 5. Analysis Populations

The following analysis sets are defined for Part 1 open-label phase and Part 2 blinded phase: Randomization Set, Full Analysis Set (FAS), Per-Protocol (PP) Set for Efficacy, Immunogenicity Subset, Per-Protocol (PP) Immunogenicity Subset, Safety Set, Solicited Safety Set, Modified Intent-to-Treat (mITT) Set, Modified Intent-to-Treat-1 (mITT1) Set.

### 5.1. Randomization Set

The Randomization Set consists of all participants who are randomized in the Part 2 of study, regardless of the participant's treatment status in the study. Participants will be analyzed according to the treatment group to which they were randomized.

### 5.2. Full Analysis Set

The Full Analysis Set (FAS) for Part 1 consists of all enrolled participants who receive at least 1 injection of IP, and the FAS for Part 2 consists of all randomly assigned participants who receive at least 1 injection of IP. Participants will be analyzed according to the treatment group for the treatment they actually received in Part 1 and will be analyzed according to the treatment group to which they were randomized in Part 2.

### **5.3. Per-Protocol (PP) Set for Efficacy**

The Per-protocol (PP) Set for Efficacy consists of all participants in the FAS who meet all the following criteria:

- a) Received planned doses of IP per schedule
- b) Complied with the 2nd dose injection timing
- c) Had no major protocol deviations that impact key or critical efficacy data
- d) Had a negative RT-PCR test for SARS-CoV-2 and negative serology test based on bAb specific to SARS-CoV-2 nucleocapsid protein at baseline

The PP Set for Efficacy in both parts will be used as the primary analysis population in the efficacy analyses unless otherwise specified. Participants will be analyzed according to the treatment group for the treatment they actually received in Part 1 and to which they were randomized in Part 2.

### **5.4. Immunogenicity Subset**

A subset of participants in the FAS will be selected for immunogenicity sampling and testing. Participants in Part 1 and 2 of the study and in different age groups who receive the same mRNA-1273 dose level may be combined for analysis.

Immunogenicity Subset consists of

- a) a subset of participants in the FAS, and
- b) have baseline (Day 1) SARS-CoV-2 status available, and
- c) have baseline and at least one post-injection antibody assessment for the analysis endpoint.

Immunogenicity Subset will be used for sensitivity analyses or supportive analysis. Participants will be analyzed according to the treatment group to which they were randomized.

**Table 2: Phlebotomy Schedule for Serology, Biomarker Sample, and CMI for Part 2 (Expansion) of the Study**

**For participants that chose to receive a booster dose under protocol Amendment 7, please see separate SAP for part 2 open-label phase and booster doses's section 8.7 appendix G for the booster dose phlebotomy schedule.**

**If Day 209/Day 394 blood draw is within 30 days of planned BD-Day 1, BD-Day 1 blood draw can be used for Day 209/Day 394.**

| Cohort  | Number of Subjects                    | Study Visit Day   |                  |                          |     |     |                                    |                                    |
|---|---------------------------------------|-------------------|------------------|--------------------------|-----|-----|------------------------------------|------------------------------------|
|   |                                       | D1  | D29  | D30
(+3)  | D43 | D57 | D209
(+30
days)  | D394
(+30
days)  |
| Phlebotomy Schedule for Serology: To be Executed Within Age Group  |                                       |                   |                  |                          |     |     |                                    |                                    |
| A   | First 176 (132 mRNA-1273: 44 placebo) | X                 | X                |                          |     | X   |                                    |                                    |
| B   | Next 176 (132 mRNA-1273: 44 placebo)  | X                 |                  |                          |     | X   | X                                  |                                    |
| C   | Next 176 (132 mRNA-1273: 44 placebo)  | X                 |                  |                          |     | X   |                                    | X                                  |
| D   | Remainder of the age group            | X                 |                  | X            |     |     |                                    |                                    |
| Phlebotomy Schedule for Cell-Mediated Immunity: To be Executed Within Each Age Group at Selected VTEU Sites only |                                       |                   |                  |                          |     |     |                                    |                                    |
| E (CMI with exploratory serology)   | 24 (18 mRNA-1273: 6 placebo)          | X                 |                  |                          | X   |     | X                                  | X                                  |

Abbreviations: CMI = cell-mediated immunity; D = day; VTEU = Vaccine and Treatment Evaluation Units.

1. On Day 1, sample must be collected prior to randomization and dosing. On Day 29, sample must be collected prior to dosing.
2. If a Day 1 (baseline) blood sample cannot be obtained in either Part 1 or Part 2, the participant will be considered either a screen failure due to inability to satisfy inclusion criterion 3 or could be scheduled for rescreening. Participants may be rescreened 1 time, either within same screening period for Part 1 or Part 2 or in a new screening period for Part 2 if the initial screening was in Part 1. If the participant is rescreened and a blood sample still cannot be obtained, then he/she will be considered a screen failure due to inability to satisfy inclusion criterion 3.
3. Serum sample from ~4 ml of blood only, to be stored for potential future use for biomarker assessment
4. If the participant decides to receive a booster dose, the BD1 blood draw (Protocol Table 15) can be used for Day 209 or Day 394 (Protocol Table 14).

## 5.5. Per-Protocol (PP) Immunogenicity Subset

Per-Protocol (PP) Immunogenicity Subset consists of all participants in Immunogenicity Subset who meet all the following criteria:

- a) Received planned doses of IP per schedule
- b) Complied with the immunogenicity window based on 2nd dose injection timing
- c) Had a negative RT-PCR test for SARS-CoV-2 and a negative serology test based on bAb specific to SARS-CoV-2 nucleocapsid protein at baseline
- d) If participants have a diagnosis of HIV, they are not receiving highly active anti-retroviral therapy (HAART)
- e) Had baseline (Day 1) and Day 57 Ab assessment for the analysis endpoint
- f) Had no major protocol deviations that impact key or critical data

The PP Immunogenicity Subset will serve as the primary population for the analysis of immunogenicity data in this study unless specified otherwise. Participants will be analyzed according to the treatment group for the treatment which they actually received in Part 1 and to which they were randomized in Part 2.

## **5.6. Safety Set**

The Safety Set of Part 1 consists of all enrolled participants and of Part 2 consists of all randomized participants who received any study injection. The Safety Set will be used for analysis of safety except for the solicited ARs. In addition, the following Safety Set is defined for each injection separately. The First (Second) Injection Safety Set consists of all subjects in the Safety Set who have received the first (second) study injection. Participants will be included in the vaccination group corresponding to the vaccination they actually received. For a participant who was randomized to placebo in Part 2 but received any dose of mRNA-1273 at any injection, the participant will be included in the mRNA-1273 group in the Safety Set.

## **5.7. Solicited Safety Set**

The Solicited Safety Set consists of all participants in the safety set who contribute any solicited AR data, i.e., have at least one post-baseline solicited safety assessment. The Solicited Safety Set will be used for the analyses of solicited ARs and participants will be included in the vaccination group corresponding to the study injection they actually received. In addition, the following Solicited Safety Set is defined for each injection separately.

The First (Second) Injection Solicited Safety Set consists of all subjects in the Solicited Safety Set who have received the first (second) study injection and have contributed any

solicited AR data from the time of first (second) study injection through the following 6 days.

Participants will be analyzed according to the vaccination group a participant received, rather than the vaccination group to which the subject was randomized. A participant who was randomized to placebo but received any dose of mRNA-1273 at any injection will be included in the mRNA-1273 group in the Solicited Safety Set.

### **5.8. Modified Intent-to-Treat (mITT) Set**

The Modified Intent-to-Treat (mITT) Set consists of all participants in the FAS who had no serologic or virologic evidence of prior SARS-CoV-2 infection (both negative RT-PCR test for SARS-CoV-2 and negative serology test based on bAb specific to SARS-CoV-2 nucleocapsid) at baseline, i.e., all FAS participants excluding those with positive or missing RT-PCR test or serology test at baseline.

Participants will be analyzed according to the treatment group to which they were randomized.

### **5.9. Modified Intent-to-Treat-1 (mITT1) Set**

The Modified Intent-to-Treat-1 (mITT1) Set consists of all participants in the mITT Set excluding those who received wrong treatment (i.e., at least one dose received that is not as randomized or planned).

Participants will be analyzed according to the treatment group to which they were randomized.

## **6. Statistical Analysis**

### **6.1. General Considerations**

The Schedule of Assessments is provided in [Appendix E](#) for Part 1 and 2 study arms 1 through 13.

**Continuous variables** will be summarized using the following descriptive summary statistics: the number of subjects (n), mean, standard deviation (SD), median, minimum (min), and maximum (max).

**Categorical variables** will be summarized using counts and percentages.

**Baseline value**, unless specified otherwise, is defined as the most recent non-missing measurement (scheduled or unscheduled) collected before the first dose of IP. For

immunogenicity tests and nasal swab tests, the baseline is defined as the most recent non-missing measurement (scheduled or unscheduled) collected before or on the date of first dose of IP (Day 1).

For the summary statistics of all numerical variables unless otherwise specified, the display precision will follow programming standards. Please see [Appendix A](#) for variable display standards.

When count data are presented, the percentage will be suppressed when the count is zero in order to draw attention to the non-zero counts. A row denoted “Missing” will be included in count tabulations where specified on the shells to account for dropouts and missing values. The denominator for all percentages will be the number of subjects in that age group and vaccination group within the analysis set of interest, unless otherwise specified.

**Baseline SARS-CoV-2 status** is determined by using virologic and serologic evidence of SARS-CoV-2 infection on or before Day 1.

Negative status at Baseline is defined as the most recent RT-PCR for SARS-CoV-2 result is negative and the most recent serology test based on bAb specific to SARS-CoV-2 nucleocapsid result is negative on or before Day 1.

Positive SARS-CoV-2 status at Baseline is defined as the most recent RT-PCR for SARS-CoV-2 result is positive and/or the most recent serology test based on bAb specific to SARS-CoV-2 nucleocapsid result is positive on or before Day 1.

**Study day relative to the first** injection will be calculated as below:

- a) study day prior to the first injection will be calculated as: date of assessment/event – date of the first injection;
- b) study day on or after the date of the first injection will be calculated as: date of assessment/event – date of the first injection + 1

**Study day relative to the most recent** injection will be calculated as below:

- a) study day prior to the first injection will be calculated as: date of assessment/event – date of the first injection;
- b) study day on or after the date of the first injection but before the second injection (if applicable) will be calculated as: date of assessment/event – date of the first injection + 1;

- c) study day on or after the date of the second injection will be calculated as: date of assessment/event – date of the second injection + 1; if study day is on the same day as the second injection, date and time will be compared with the second injection date and time.

**For calculation regarding antibody value**, antibody values reported as LLOQ will be replaced by  $0.5 \times \text{LLOQ}$ . Values that are greater than the upper limit of quantification (ULOQ) will be converted to the ULOQ if actual values are not available, and actual values will be used if available. Missing results will not be imputed.

The following **analysis periods or stages for safety analyses** will be used in this study:

- Up to 28 days after any vaccination: this stage starts at the day of each vaccination and continue through the earliest date of (the day of each vaccination and 27 subsequent days, next vaccination [if applicable]). This analysis period will be used as the primary analysis period for safety analyses including unsolicited AE, except for solicited AR, unless specified otherwise.
- Follow-up analysis period:

For unsolicited AE or assessments that will be collected throughout the study, this analysis period starts from 28 days after the last injection date (i.e. the day of last injection + 28 days, regardless of number of injections received) and continues until the earliest date of (study completion, discontinuation from the study, or death).

For assessments that will be collected at study visits, if a subject receives two injections, this stage starts from the day after Day 57 visit and continues until the earliest date of (study completion, discontinuation from the study, or death); if a subject receives first injection only, this stage starts from the day after Day 29 visit and continues until the earliest date of (study completion, discontinuation from the study, or death).

- Overall period (throughout the study): this analysis period starts at the first injection on Day 1 and continues through the earliest date of (study completion, discontinuation from the study, or death).

**Unscheduled visits:** Unscheduled visit measurements will be included in analysis as follows:

- In scheduled visit windows per specified visit windowing rules.
- In the derivation of baseline/last on-treatment measurements.
- In the derivation of maximum/minimum on-treatment values and maximum/minimum change from baseline values for safety analyses.
- In individual subject data listings as appropriate.

**Visit windowing rules:** The analysis visit windows for protocol-defined visits are provided in [Appendix B](#).

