#### **Summary by age group:**

All analyses and data summaries/displays will be provided by vaccination group for each age cohort (6 months to < 2 years, 2 years to < 6 years, and 6 years to < 12 years), unless otherwise specified. Participants in Part 1 and 2 of the study and in different age groups who receive the same mRNA-1273 dose level may be combined for safety analysis.

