### **6.3. Safety Analysis**

Safety and reactogenicity will be assessed by clinical review of all relevant parameters including solicited ARs (local and systemic), unsolicited AEs, SAEs, MAAEs, AESIs, AEs leading to withdrawal from study vaccine and/or study participation, and physical

examination findings. Solicited ARs and unsolicited AEs will be coded by SOC and PT according to the MedDRA. Two modified versions of The Toxicity Grading Scale for Healthy Adult and Adolescent Volunteers Enrolled in Preventative Vaccine Clinical Trials (DHHS 2007) are used in this study for solicited ARs as presented in protocol section 7.4.3's Table 8 and 9; Table 8 is the pediatric toxicity scale used for children older than 36 months, and Table 9 is the infant/toddler toxicity scale used for children 6 to 36 months of age, inclusive

All safety analyses will be based on the Safety Set, except summaries of solicited ARs which will be based on the Solicited Safety Set. All safety analyses will be provided by age and vaccination group unless otherwise specified.

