### **6.3.2. Solicited Adverse Reactions**

An AR is any AE for which there is a reasonable possibility that the test product caused the AE. The term “Solicited Adverse Reactions” refers to selected signs and symptoms occurring after injection administration during a specified post-injection follow-up period

(day of injection and 6 subsequent days). The solicited ARs are recorded by the subject in eDiary. The occurrence and intensity of selected signs and symptoms is actively solicited from the participant during a specified post-injection follow-up period (day of injection and 6 subsequent days), using a pre-defined checklist (i.e., solicited ARs).

The following local ARs will be solicited by the eDiary: pain at injection site, erythema (redness) at injection site, swelling (hardness) at injection site, localized axillary swelling or tenderness ipsilateral to the injection arm, and groin or underarm swelling or tenderness ipsilateral to the side of injection.

The following systemic ARs will be solicited by the eDiary: headache, fatigue, myalgia (muscle aches all over the body), arthralgia (aching in several joints), nausea/vomiting, fever, chills, irritability/crying, sleepiness, and loss of appetite.

The AR categories are different for younger population between Age 37 months to <12 years and Age 6 months to  $\leq$  36 months. Details presented in Table 8 and 9 in the protocol.

The solicited ARs will be graded based on the grading scales presented in Table 8 and 9 in the protocol, modified from the Toxicity Grading Scale for Healthy Adult and Adolescent Volunteers Enrolled in Preventative Vaccine Clinical Trials (DHHS 2007). Investigator will assess Grade 4 events (with exception of fever).

If a solicited local or systemic AR continues beyond 7 days post injection, the participant's parent(s)/ LAR(s) will be prompted to capture details of the solicited local or systemic AR in the eDiary until it resolves or the next IP injection occurs, whichever occurs first.

All solicited ARs (local and systemic) will be considered causally related to injection.

After booster doses with mRNA-1273.214, local or systemic ARs will only be reported on the eCRF if they are medically attended, considered serious or lead to discontinuation from the study. No eDiaries will be used after booster doses with mRNA-1273.214.

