Analyses of solicited ARs will be provided by age and treatment group for each injection (first or second) based on the associated subset of Solicited Safety Set, i.e. First (Second) Injection Solicited Safety Set; and for any injection based on the Solicited Safety Set, unless otherwise specified.

The number and percentage of subjects who reported each individual solicited local AR (has a toxicity grade of Grade 1 or greater) and solicited systemic AR (has a toxicity grade of Grade 1 or greater) during the 7-day follow-up period after each injection will be tabulated by age group, vaccination group, toxicity grade, and injection. The number and

percentage of subjects who reported each individual solicited AR will also be summarized by age group, vaccination group, toxicity grade, days of reporting and injection.

The number and percentage of subjects experiencing fever (a temperature greater than or equal to 38.0°C/100.4°F by the oral, axillary, or tympanic route) by toxicity grade will be provided.

A two-sided 95% exact confidence interval (CI) using the Clopper-Pearson method will be provided for the percentage of subjects who reported any solicited local AR, solicited systemic AR, or any solicited AR.

The onset of individual solicited AR is defined as the time point after each injection at which the respective solicited AR first occurred. The number and percentage of subjects with onset of individual solicited AR will be summarized by age group, vaccination group, study day relative to the corresponding injection (Day 1 through Day 7), and injection.

The duration will be calculated as the end date/day of the solicited AR event – start date/day of the solicited AR event + 1, regardless of whether it is intermittent or continued. If the solicited AR continues beyond 7 days, the days a solicited AR is reported after 7 days will be included (e.g., an event that lasted 5 days in the first 7 days post injection and 3 days beyond 7 days post injection, the duration will be reported as 8 (5+3) days.)

Solicited ARs collected on eDiary and those collected on reactogenicity aCRF will be provided in a listing, and the maximum grade from eDiary and aCRF will be presented. All solicited ARs that continue beyond 7 days post injection will be presented in separate data listings.

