6. Post-dosing, participants will have a 30-minute observation period. If any concerning symptoms occur, investigator may check vital signs during this period (however, no routine vital signs necessary after vaccination, except temperature as per 30-minute eDiary, if no concerning symptoms).
7. An unscheduled visit may be prompted by reactogenicity issues or new or ongoing AEs.
8. The nasal swab sample must be collected prior to injection at the BD-1 visit.
9. Trained study personnel will call all participants to collect information relating to any unsolicited AEs, MAAEs (including any signs and symptoms of COVID-19), AESI, AEs leading to withdrawal, SAEs, information on concomitant medications associated with those events, and any nonstudy vaccinations.
10. Age at time of enrollment determines which eDiary the participant will use. Diary entries will be recorded by the participant at approximately 30 minutes after injection while at the study site with instruction provided by study staff. Study participants will continue to record entries in the eDiary each day after they leave the study site, preferably in the evening, on the day of injection and for 6 days following injection. If a solicited local or systemic AR continues beyond Day 7 after vaccination, the participant will be prompted to capture details of the solicited local or systemic AR in the eDiary until the AR resolves; capture of details of ARs in the eDiary should not exceed 28 days after vaccination. Adverse reactions recorded in eDiaries beyond Day 7 should be reviewed either via telephone call or at the following study visit. Review of eDiary will occur on BD-D8 and BD-D29.
11. All concomitant medications relevant to or for the treatment of an SAE, AESI, or MAAE will be recorded from screening through the final visit. Non-study COVID-19 vaccines will be recorded through EOS.

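### In the 2 to <6 years group, solicited reactions asked in only one diary version are divided by a set that includes children never asked about them, so their rates print too low

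*SAP*

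**What the plan says.** The document holds two plans: one for the Part 1 open-label and Part 2 blinded phases (here, the main SAP) and one for the Part 2 open-label phase, boosters and Part 3 (the booster SAP).

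- **Endpoint.** Main SAP Section 3.1 lists solicited local and systemic reactions over 7 days first among the primary safety endpoints.
- **Default denominator.** Main SAP Section 6.1: "The denominator for all percentages will be the number of subjects in that age group and vaccination group within the analysis set of interest". The sentence closes by leaving room for a different base where one is stated.
- **Display groups.** Summaries use "each age cohort (6 months to < 2 years, 2 years to < 6 years, and 6 years to < 12 years" as display units, again by default. None of these groups breaks at 36 months.
- **Two scales and two item lists.** Section 6.3: "Table 8 is the pediatric toxicity scale used for children older than 36 months", while "Table 9 is the infant/toddler toxicity scale used for children 6 to 36 months of age, inclusive". Section 6.3.2: "The AR categories are different for younger population between Age 37 months to <12 years and Age 6 months to" (the upper limit that follows is 36 months, inclusive). That section then prints one merged list of reactions without assigning items to a version.
- **Analysis set.** Section 5.7 admits a child who contributes any solicited data. The First and Second Injection Solicited Safety Sets require data after that injection. Membership is not defined per reaction.
- **Tabulation.** Under Section 6.3.2 each individual reaction "will be tabulated by age group, vaccination group, toxicity grade, and injection".
- **Booster.** Booster SAP Sections 6.1, 6.3 and 6.3.2 follow the same pattern. Its Appendix F, footnote 10, adds: "Age at time of enrollment determines which eDiary the participant will use".

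**The concern.** The 36/37-month cut falls inside one display group only, 2 to <6 years. In that group the injection-specific Solicited Safety Set mixes children who answered two different item lists. A 30-month-old never asked an older-child item stays in the denominator for that item and can never be in its numerator. A 5-year-old does the same for an infant/toddler item. Section 6.1 says other missing data are not imputed, yet this denominator in effect imputes no reaction for every child not asked.

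The output of this endpoint is a set of absolute frequencies of individual reactions. The error has one direction: reactions look rarer than they were. The by-grade, by-day and onset-day tables of Section 6.3.2 inherit it for the same items. Optional pooling of age groups that share a dose level (Section 6.1) would carry it into the pooled tables.

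**Working it through.** The plan gives no figure on this point, so there is nothing to reproduce. The check has two steps.

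**1. Is the default overridden?** The main SAP does write its own percentage base where it wants one: Section 6.2.1 for disposition and Section 6.3.1 for unsolicited events. For solicited reactions, Section 6.3.2 names the Solicited Safety Set and its per-injection subsets and stops there. Neither Section 5.7 nor Section 6.3.2 limits a reaction's denominator to children asked about it, and nothing splits the 2 to <6 years group at 36 months. The default therefore applies to these rows.

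**2. How large is the effect?** Let *s* be the share of the 2 to <6 years injection-specific set that used the infant/toddler diary, and *p* the true rate among children asked.

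- Infant/toddler-only item: printed rate = *s* × *p*
- Older-only item: printed rate = (1 − *s*) × *p*

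The plan does not give *s*. Assuming uniform ages over 24 to <72 months (48 months):

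- infant/toddler diary up to exactly 36 months: 12/48 = 25.0%
- infant/toddler diary through the 36th completed month: 13/48 = 27.1%

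The next table varies *s*, with true rates of 60% (infant/toddler-only) and 30% (older-only) assumed for illustration.

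| *s* | Infant/toddler-only factor | Older-only factor | True 60%, infant/toddler-only, prints as | True 30%, older-only, prints as |
|---|---|---|---|---|
| 0.15 | 0.15 | 0.85 | 9.0% | 25.5% |
| 0.25 | 0.25 | 0.75 | 15.0% | 22.5% |
| 0.271 | 0.271 | 0.729 | 16.2% | 21.9% |
| 0.35 | 0.35 | 0.65 | 21.0% | 19.5% |
| 0.50 | 0.50 | 0.50 | 30.0% | 15.0% |

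In counts, take the planned ceiling of 3,000 vaccine recipients (Study Arm 10) and *s* = 13/48. About 812 children use the infant/toddler diary and 2,188 the other.

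- Infant/toddler-only item: 487/812 = 60.0% among those asked, but 487/3,000 = 16.2% under the default.
- Older-only item: 656/2,188 = 30.0% among those asked, but 656/3,000 = 21.9% under the default.

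**Between arms.** With randomization the expected *s* is the same in both arms. The ratio (*s* × *p*₁)/(*s* × *p*₀) = *p*₁/*p*₀ is then preserved. A difference is scaled by the same factor as the rates: an assumed 15-point difference in an older-only item would read 15 × 0.729 = 10.9 points.

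**The case against.** The strongest reply is that Section 6.1 makes only a default, open to other specification, and leaves layout to table shells that are not shown. The authors plainly knew that the categories differ by age, since Section 6.3.2 says so, and the shells may already use item-specific denominators. That stands as a limit. It cannot be said that any produced table is wrong, only that a programmer following the text would produce the diluted rate.

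It is also fair that reach and size depend on matter not at hand. The item assignment is in protocol Tables 8 and 9, the age mix is unknown, 3,000 is a ceiling, and the true rates above are illustrations.

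A reader might infer more than the plan supports:

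- **That the denominator is every child in the age group.** It is the injection-specific Solicited Safety Set. That set still mixes both diaries.
- **That the whole endpoint is understated.** It is not. Section 6.3.2 plans Clopper-Pearson intervals only for any local, any systemic and any solicited reaction. Both diaries feed these rows. Items common to both diaries are not diluted either.
- **That the planned vaccine-placebo comparison is biased.** Section 6.3.2 plans no between-arm test or difference for solicited reactions, and ratios are roughly preserved. Only a difference that a reader computes would shrink.
- **That the booster rules contradict each other.** The booster SAP states the scale by age without saying age at booster, so this does not conflict with a diary fixed by age at enrollment. Scope there is also small. Appendix F covers Study Arms 1 through 9, which for enrolled 2 to <6 year-olds means the Part 1 arms (about 225 children). No eDiary is used after mRNA-1273.214, and Part 3 enrolls only 6 to <12 years.

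**Conclusion.** The point holds in limited form. As written, the main SAP divides single-diary reactions in the 2 to <6 years group by a set containing children never asked about them. Their absolute percentages, at any grade and at Grade 3, are understated in proportion to the share not asked. With uniform ages assumed, the loss is about 25-27% of the true rate for older-only items and about 73-75% for infant/toddler-only items. For *s* from 0.15 to 0.50, the loss is 15-50% and 50-85% respectively.

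This rests on Section 6.3.2's statement that categories differ by age, on the absence of any override in the text, and on an assumed age mix. It should be corrected because it touches a primary safety endpoint and always makes reactions look rarer. It does not affect the immunobridging tests or the definitions of the analysis sets.

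**What to change.** In main SAP Section 6.3.2, add a rule for individual solicited reactions (any grade, by grade, by day and onset). Either of these would do:

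1. Present 2 to <6 years, and any pooled age groups, by the diary version actually completed (6-36 months; 37 months to <12 years).
2. Set each reaction's denominator to the children in the injection-specific Solicited Safety Set whose diary asked that item, and print that number in the row.

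Keep the whole-group denominator for the composite rows and for items common to both diaries. Put the same wording in booster SAP Section 6.3.2 for the Part 1 2 to <6 years recipients of the mRNA-1273 booster, keyed to the diary used rather than age at booster.

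The cost is SAP wording and a shell change on data already collected. The downside is smaller denominators, and so less precise percentages, in the 24-36 month rows.
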